Topical Proparacaine Eye Drops
to Improve the Experience of
Patients Undergoing
Intravitreal Injections

NCT# 02951351

September 07, 2016

STUDY NAME

INTRODUCTORY STATEMENT

The specific aims of this study are to compare patient experience with and without a proparacaine drop after povidone iodine. To ensure the extra drop does not interfere with antisepsis, conjunctival cultures will be obtained from patients undergoing intravitreal injection before and after the application of the extra eye drop.

A. Background information:

1. Intravitreal injections

Intravitreal injections are used to treat patients with many ocular conditions including: exudative age related macular degeneration, endophthalmitis, CMV retinitis, forms of choroidal neovascularization, e.g. diabetic retinopathy, and macular edema.

2. A feared complication, endophthalmitis

Endophthalmitis is a post-injection complication with great morbidity. A comprehensive review published in 2004 outlining the risk of endophthalmitis after intravitreous injection found a 0.2% prevalence per injection, which increased to 0.6% prevalence for injection with triamcinolone acetonide. All other injected medications had a risk of 0.1% per injection.[1] A 2011 study published in *Retina* reported that 1 out of every 4000 to 8000 injections of anti-VEGF medications results in endophthalmitis.[2] Finally, a study using a Medicare database found that of 41,000 injections, the rate of post-injection endophthalmitis was about 0.09% per injection.[3]

The specific bacteria that cause post-injection endophthalmitis have been reported in a study by McCannel as most commonly coagulase-negative *Staphylococcus* species in 65.4% of cases where a bacterium was identified. *Streptococcus* species were identified in 30.8% of endophthalmitis cases; most commonly viridans group streptococci (VGS), *S. salivarius*, and *S. mitis*. [4]

3. Preventative measures

To prevent endophthalmitis, sterilization is attempted before injections using 5% povidone-iodine (PI), Betadine, which has been demonstrated to be as effective as topical antibiotics. [5] Povidone iodine's use prior to IVI is supported by a number of studies.[6, 7] Apt *et al.* demonstrated that one drop of povidone iodine administered preoperatively reduced bacterial colonies in conjunctival cultures by 91% versus 33% for control eyes.[8] Isenberg demonstrated that preoperative administration of povidone iodine was as effective as neomycin, polymyxin B, and gramicidin (Neosporin, Johnson & Johnson, New Brunswick, NJ) ophthalmic solution given three consecutive days prior to surgery in reducing conjunctival cultures.

STUDY NAME

Neosporin plus povidone iodine was more effective than either alone, leading to a 99.9% decreased colony count.[6] Overall, povidone iodine is nontoxic to the eye in the appropriate concentrations, has a broad antimicrobial spectrum (including bacteria, fungi, protozoa, and viruses), has a low propensity to select for bacterial resistance, is inexpensive, and is widely available.[9]

4. Antimicrobial properties of proparacaine

The antibacterial properties of proparacaine have been previously reported. A study on the effects of topical anesthetics on bacteria using a disk diffusion technique studied proparacaine and 0.5, 0.25, and 0.125% concentrations found that proparacaine inhibited the growth of *Staphylococcus aureus* at 1,250 µg/mL, and inhibited *Pseudomonas aeruginosa* growth at 2,500 µg/mL. [10] Proparacaine has also been demonstrated to have antimicrobial properties against *Staphylococcus epidermidis* and viridans group streptococci (VGS). It has been shown to reduce the number of culture-positive eyes, with 4 of 40 eyes being culture-positive after proparacaine, versus 12 of 36 eyes being culture-positive after receiving control solution, containing only preservative.[11] The mechanism by which proparacaine acts as an antimicrobial has been studied; it is thought to disrupt bacterial cell membranes causing permeability and lysis.[12, 13] Finally, benzalkonium chloride, the preservative component of proparacaine, has been demonstrated to have antimicrobial effects, with an *in vitro* study showing that benzalkonium chloride inhibits *S. aureus* growth.[14]

5. Background research (see attachment):

We have previously conducted a study comparing the minimum inhibitory concentrations (MICs) of topical anesthetics utilized prior to intravitreal injection (proparacaine, tetracaine, lidocaine), preservative benzalkonium chloride, and antiseptic povidone iodine for bacteria causing endophthalmitis. Lidocaine (8.53×10^{-5} mol/mL) had MICs of 4.27×10^{-5} - 8.53×10^{-5} mol/mL, and tetracaine (1.89×10^{-5} mol/mL) had MICs of 9.45×10^{-6} mol/mL for all isolates. Proparacaine (1.7×10^{-5} mol/mL) had MICs of 1.32 to 5.3×10^{-7} mol/mL, 4.25×10^{-6} mol/mL for *S. epidermidis*, VGS, respectively). Benzalkonium chloride (3.52×10^{-7} mol/mL) had MICs of 1.86×10^{-9} - 1.1×10^{-8} mol/mL, 4.40×10^{-8} mol/mL for *S. epidermidis*, VGS, respectively. Povidone iodine (1.37×10^{-4} mol/mL) had MICs of 2.14×10^{-6} - 4.28×10^{-6} mol/mL, 8.56×10^{-6} mol/mL for *S. epidermidis*, VGS, respectively.

Proparacaine was the anesthetic with lowest MICs, lower than that of povidone iodine. Benzalkonium chloride had a lower MIC than proparacaine. All tested topical anesthetics and

STUDY NAME

povidone iodine inhibited growth of *S. epidermidis* and VGS at commercially available concentrations.

We also previously studied synergy and antagonism for all isolates using povidone iodine at 25% and 50% of its MIC. Proparacaine with povidone iodine demonstrated synergy against all VGS studied and additivity or indifference against all strains of *S. epidermidis*. Benzalkonium chloride with povidone iodine demonstrated synergy against 80% of *S. epidermidis* isolates studied and additivity or indifference against all VGS.

6. Significance

Intravitreal injections are one of the most common procedures performed by ophthalmologists. As its indications expand and the population with conditions treated with intravitreal injections grows, it is beneficial to know how to prevent complications such as endophthalmitis. It is often the case that patients will have a painful injection and refuse additional vision-saving treatment. A study to compare the timing of eye drops could help improve patient experience. It will also be important to compare conjunctival cultures of patients treated with proparacaine alone and with povidone iodine may be informative from an antimicrobial standpoint.

From the perspective of patient experience, recent studies have demonstrated great patient dissatisfaction with the application of povidone iodine. In a study by van Asten *et al.*, more patients (26%) reported povidone iodine application than intravitreal injection (10%) to be the most bothersome part of the intravitreal injection process. [15] The current expert guidelines for IVI stress the importance of 5.0% povidone iodine use. The guidelines recommend that povidone iodine should be the last agent applied before performing injections, and physicians should be careful as the anesthetic may interfere with the contact of povidone iodine to the conjunctival surface. Therefore, the guidelines recommend applying povidone iodine before and after topical anesthetic. It is possible, though, that the antimicrobial effects of proparacaine allow it to be applied following the povidone iodine in patients who find PI unpleasant.

It would also be useful to determine the impact of proparacaine and povidone iodine on each other. In our preliminary studies, proparacaine with povidone iodine demonstrated synergy against all VGS studied. Benzalkonium chloride with povidone iodine demonstrated synergy against 80% of *S. epidermidis* isolates studied. These results may influence choice of topical anesthetic.

STUDY NAME

Proparacaine

(<http://www.micromedexsolutions.com/micromedex2/librarian/PFDefaultActionId/evidenceexpert.DoIntegratedSearch#>) is a topical anesthetic commonly used prior to intravitreal injections. This proposal recommends deviating from the usual protocol of one drop of proparacaine prior to povidone iodine to adding an addition drop of proparacaine after the povidone iodine as proparacaine has been demonstrated to have antimicrobial properties and assist with patient comfort.

GENERAL INVESTIGATIONAL PLAN

[figure not shown]
Study rationale- Intravitreal injections are one of the most common procedures performed by ophthalmologists. The study endpoints are to improve the patient experience while minimizing negative outcomes, one of the most worrisome of these outcomes is endophthalmitis. The study will address first patient experience and ensure that the treatment is not detrimental to antisepsis.

Indication- To compare the effects of proparacaine before and after povidone iodine application on patient experience, and to compare bacterial colonies in conjunctival cultures obtained from patients undergoing intravitreal injection to ensure adequate antisepsis.

General approach/Treatment plan (See figure 1)- The study will take place during intravitreal injections. The anticipated study is as follows: After a procedural time out to verify patient, agent, and laterality, proparacaine will be applied to the ocular surface. A conjunctival culture will then be obtained followed by the application of povidone-iodine to the eyelashes and eyelid margins. The eyelids will then be retracted away from the intended injection site for the duration of the procedure. At this point, half of the patients will be randomized to receive 5% povidone-iodine drop to the conjunctival surface followed by conjunctival culture then re-application of 5% povidone-iodine drop to the conjunctival surface. A needle will then be inserted perpendicular to the sclera, 3.5-4.0 mm posterior to the limbus between the vertical and horizontal rectus muscles. The other half of patients will undergo application of another drop of topical anesthetic followed by conjunctival culture. After the culture, this group of patients will have 5% povidone iodine applied to the conjunctival surface. A needle will then be inserted perpendicular to the sclera, 3.5-4.0 mm posterior to the limbus between the vertical and horizontal rectus muscles.

STUDY NAME

Figure 1

** the circles highlight deviations from the typical protocol

Human subjects

Sixty patients (male and female) undergoing intravitreal injection who do not have active eye infections will be enrolled after undergoing informed consent.

Exclusion criteria: 1. Age less than 18. 2. Patients with active eye infections

[figure not shown]
The main risk encountered by human subjects would be infection given extra manipulation prior to intravitreal injection. These risks will be minimized by using sterile culture techniques. All cultures will be followed by application of povidone iodine to comply with current recommendations to sterilize conjunctiva prior to intravitreal injection. It is also possible that patients will experience increased discomfort due to the conjunctival cultures. Per the protocol, cultures will follow topical anesthetic application.

Data collection:

Conjunctival cultures will be incorporated into the current intravitreal injection procedure

STUDY NAME

followed by Mayo Clinic.:

a. Conjunctival cultures

Bacterial cultures will be performed from conjunctival samples. Bacterial speciation will be performed on any bacteria that grows using the usual procedure to determine the bacterial species collected by the study.

b. Proparacaine Eye drops

Proparacaine 0.5% with preservative benzalkonium chloride 0.01% (Akorn) will be analyzed for its effect on bacterial growth *in vivo* with and without povidone iodine.

c. Data analysis and interpretation

Whether cultures are positive or negative will be compared between groups. Outcomes will also be measured by comparing the semiquantitative number of bacterial cultures (the microbiology lab will report cultures as 1+ through 4+) according to the Mayo Clinic Microbiology laboratory protocol. Patients who have positive cultures will have specific bacterial species determined which will also be analyzed. Demographic characteristics will be recorded including date of

STUDY NAME

birth and sex. Information surrounding the indication for injection will also be obtained as well as type of medication injected and number of previous injections. Finally, medication data will be included with specific focus on antibiotics—topical or systemic and eye drops.

In addition, patients will complete the previously detailed survey regarding their experience. Patient experience will be compared between groups and to existing data from this previously utilized survey described in PMID: 25901838.

Human subjects

Sixty patients (male and female) undergoing intravitreal injection who do not have active eye infections will be enrolled after undergoing informed consent.

Exclusion criteria: 1. Age less than 18. 2. Patients with active eye infections

The main risk encountered by human subjects would be infection given extra manipulation prior to intravitreal injection. These risks will be minimized by using sterile culture techniques. All cultures will be followed by application of povidone iodine to comply with current recommendations to sterilize conjunctiva prior to intravitreal injection. It is also possible that patients will experience increased discomfort due to the conjunctival cultures. Per the protocol, cultures will follow topical anesthetic application.

Treatment plan:

After a procedural time out to verify patient, agent, and laterality, proparacaine will be applied to the ocular surface. A conjunctival culture will then be obtained followed by the application of povidone-iodine to the eyelashes and eyelid margins. The eyelids will then be retracted away from the intended injection site for the duration of the procedure. At this point, half of the patients will be randomized to receive 5% povidone-iodine drop to the conjunctival surface followed by conjunctival culture then re-application of 5% povidone-iodine drop to the conjunctival surface. A needle will then be inserted perpendicular to the sclera, 3.5-4.0 mm posterior to the limbus between the vertical and horizontal rectus muscles. The other half of patients will undergo application of another drop of topical anesthetic followed by conjunctival culture. After the culture, this group of patients will have 5% povidone iodine applied to the conjunctival surface. A needle will then be inserted perpendicular to the sclera, 3.5-4.0 mm posterior to the limbus between the vertical and horizontal rectus muscles.

STUDY NAME

Safety

The current protocol for intravitreal injections requires that patients be treated with povidone iodine immediately prior to intravitreal injection for antisepsis. The protocol for this study will not deviate from the standard protocol in that way. The safety of the study will be monitored by the PI. If more than 4 patients are noted post-procedurally to require additional return visits for conjunctival irritation or infection, the study will be discontinued.

3. Turan KE, **[name]**, Brodsky MC. Incipient white dot fovea syndrome in a child. *J AAPOS*. 2014 Aug;18(4):391-3. doi: 10.1016/j.jaapos.2014.02.007. Epub 2014 Jun 7.

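### As written, the second culture does not test a proparacaine drop given after povidone-iodine, and with no interval or criterion at about 30 eyes per arm it cannot ensure antisepsis

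*Combined protocol and SAP*

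**What the plan says.** The Introductory Statement sets the aim as to "compare patient experience with and without a proparacaine drop after povidone iodine". Section 6, Significance, describes the departure from usual practice as "adding an addition drop of proparacaine after the povidone iodine", and reports the guideline caution that "physicians should be careful as the anesthetic may interfere with the contact of povidone iodine to the conjunctival surface".

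Three places give the cultures the task of excluding harm. The Introductory Statement says "To ensure the extra drop does not interfere with antisepsis, conjunctival cultures will be obtained from patients undergoing intravitreal injection before and after" the extra drop. The Study rationale says "The study will address first patient experience and ensure that the treatment is not detrimental to antisepsis". The Indication paragraph says "to compare bacterial colonies in conjunctival cultures obtained from patients undergoing intravitreal injection to ensure adequate antisepsis".

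Two other places describe a different comparison. Section 6, Significance, wants to "compare conjunctival cultures of patients treated with proparacaine alone and with povidone iodine". Section b, Proparacaine Eye drops, speaks of the effect on bacterial growth "with and without povidone iodine".

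The only analysis text is section c, Data analysis and interpretation. It plans a between-group comparison of culture positivity and of the 1+ to 4+ grade, with species also analyzed. It gives no test, significance level, interval, margin or acceptance criterion. The Human subjects section gives 60 patients without justification.

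**The concern.** There are two problems, and the more basic one is the sequence. If the second culture in the extra-drop arm is taken before conjunctival povidone-iodine, it cannot show whether the extra drop alters what povidone-iodine does on the conjunctiva. The arms differ in two respects at that moment, the second drop and the conjunctival povidone-iodine, so the contrast does not isolate the drop.

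The second problem holds under any order. A claim to ensure that something is not harmful is a claim that a harmful difference has been excluded. The plan names no result that would support it, and a non-significant difference between two small arms does not.

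At stake is the validity of the antisepsis conclusion. The culture result is one support for later use of the drop, alongside the inhibitory-concentration, synergy and earlier culture data in the background sections.

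**Working it through.** **Sequence.** General approach/Treatment plan and the later Treatment plan give the same order:

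| Step | Comparison arm | Extra-drop arm |
|---|---|---|
| 1 | Proparacaine | Proparacaine |
| 2 | First culture | First culture |
| 3 | Povidone-iodine to lashes and lid margins | Same |
| 4 | Povidone-iodine to conjunctiva | Second anesthetic drop |
| 5 | Second culture | Second culture |
| 6 | Povidone-iodine to conjunctiva again | Povidone-iodine to conjunctiva |
| 7 | Injection | Injection |

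At step 5 the comparison arm has had one proparacaine drop plus conjunctival povidone-iodine. The extra-drop arm has had two drops and no conjunctival povidone-iodine. Neither arm is cultured after step 6, so no culture in the extra-drop arm reflects proparacaine and conjunctival povidone-iodine together.

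**Precision: inputs.** 60 patients, half per arm (Human subjects; General approach/Treatment plan): 60/2 = 30. The 60 cannot be reproduced, because no rate, effect, level, power or margin is given. Assumptions: two-sided 5%, 95% intervals, no dropout. The figures below cover unadjusted second-culture positivity only. Grade, species and the first culture are not quantified.

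**Largest non-significant split against 0/30 in the comparison arm.**

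Uncorrected chi-square, N(ad-bc)²/(product of the four margins):
- 3 v 0: 60 × (3×30)² / (30×30×3×57) = 486,000/153,900 = 3.16, p = 0.076.
- 4 v 0: 60 × (4×30)² / (30×30×4×56) = 864,000/201,600 = 4.29, p = 0.038.
- The limit is therefore 3/30.

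Fisher, two-sided, which for x v 0 in equal arms is 2·C(30,x)/C(60,x):
- 5 v 0: 2 × 142,506/5,461,512 = 0.052.
- 6 v 0: 2 × 593,775/50,063,860 = 0.024.
- The limit is therefore 5/30.

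**95% Newcombe interval** for the difference d = p1 - p2 (extra-drop arm minus comparison arm), from Wilson limits (l, u) for each arm:
- lower = d - √[(p1 - l1)² + (u2 - p2)²]
- upper = d + √[(u1 - p1)² + (p2 - l2)²]

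Wilson limits: 0/30 gives 0 to 0.1135 (upper = 3.8415/33.8415); 3/30 gives 0.0346 to 0.2562; 5/30 gives 0.0734 to 0.3356.

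- 3 v 0: lower = 0.1000 - √(0.0654² + 0.1135²) = -0.031; upper = 0.1000 + 0.1562 = 0.256. Interval -3.1 to +25.6 points.
- 5 v 0: lower = 0.1667 - √(0.0933² + 0.1135²) = +0.020; upper = 0.1667 + 0.1690 = 0.336. Interval +2.0 to +33.6 points, which excludes zero.
- 0 v 0: ±√(0.1135²), so the upper limit is +11.4 points.

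**Smallest upper limit.** Over all outcomes in which the extra-drop arm has at least as many positives as the comparison arm, the smallest 95% Newcombe upper limit is +11.4 points, at 0 v 0 (and equally at 30 v 30). Equal non-zero counts give wider limits: 1 v 1 gives +13.6 and 3 v 3 gives +16.9.

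**The case against.** The strongest reply on sequence is that the contrast may be intended. Section 6 and section b both describe proparacaine with and without povidone-iodine, which fits the written order, and the missing Figure 1 may clarify it. The extra drop also does follow povidone-iodine in one sense, since lids and lashes have been treated. This stands to the extent that the order cannot be called a mistake. It does not rescue the stated question, because the guideline caution that the protocol reports concerns povidone-iodine on the conjunctival surface.

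On precision, patient experience comes first in this study, *ensure* is purpose wording, and the baseline culture and the grade could add information. That is fair, and it limits the severity. But grade and species have no criterion either, and three separate statements use *ensure*.

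Some stronger readings are not supported:

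- A reader might infer that 5/30 v 0/30 would simply be missed. That depends on the test: uncorrected chi-square gives p=0.020, and the Newcombe interval excludes zero. The plan names no test.
- A reader might take +11.4 points as the best attainable limit. It is the minimum only when the extra-drop arm has at least as many positives; 0 v 1 gives +8.3.
- A reader might infer that the sponsor will report p>0.05 as proof of antisepsis. The analysis text does not say so. It simply offers no other basis for the claim.
- A reader might infer that enrolled patients go without conjunctival povidone-iodine. Both arms receive it after the second culture and before injection.

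**Conclusion.** The point holds, and should be addressed. Followed as written, the second culture compares proparacaine without prior conjunctival povidone-iodine against povidone-iodine, and so does not answer whether a drop given after povidone-iodine interferes with antisepsis. Whether that order is intended cannot be settled from the text without Figure 1.

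Independently of the order, no stated result could support *ensure*. A result declared non-significant could be compatible with an increase of 25.6 points (chi-square) or 33.6 points (Fisher) when the comparison arm has no positives. If the extra-drop arm does no better than the comparison arm on the observed count, an increase of 11 points is never excluded. These sizes rest on the assumed 30 per arm, two-sided 5% level and Newcombe method. They describe whichever contrast the second culture turns out to measure; they do not measure interference itself.

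**What to change.** 1. Begin with the sequence. Reconcile the Introductory Statement and the section 6 and Study rationale wording on a drop after povidone-iodine with General approach/Treatment plan, Treatment plan, section b, and the other comparison described in section 6. The points to settle are the order of extra drop, second culture and conjunctival povidone-iodine, and which contrast the second culture estimates. This review does not choose an order.

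2. Add to section c, Data analysis and interpretation: *The risk difference in second-culture positivity (extra-drop arm minus comparison arm) will be reported with a 95% Newcombe confidence interval, and the antisepsis conclusion will be stated as the largest increase not excluded; p>0.05 on positivity, grade or species will not be reported as showing no interference.*

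3. In the Introductory Statement, Study rationale and Indication, replace the *ensure* wording with: *estimate the difference in conjunctival culture positivity between the two arms*, naming the contrast settled in step 1. If the order in the treatment plan text is the one carried out, label the contrast as proparacaine without prior conjunctival povidone-iodine versus povidone-iodine, and do not present it as evidence about a drop given after povidone-iodine.

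The cost is one interval, three reworded sentences and a less favourable stated claim. Steps 2 and 3 add no patients or procedures. The interval alone does not resolve the sequence question; only step 1 does.

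### As written, the second culture in the extra-drop arm precedes any conjunctival povidone-iodine drop, so the cultures cannot show whether proparacaine given after povidone-iodine interferes with antisepsis

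*Combined protocol and SAP*

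**What the plan says.** The Introductory Statement gives the purpose of the cultures as "To ensure the extra drop does not interfere with antisepsis", and says that "conjunctival cultures will be obtained from patients undergoing intravitreal injection before and after the application of the extra eye drop". Section A.6 (Significance) describes the intervention as "adding an addition drop of proparacaine after the povidone iodine". It reports the guideline concern behind the check: "the anesthetic may interfere with the contact of povidone iodine to the conjunctival surface".

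The procedure is set out under General approach/Treatment plan and repeated in the same words under Treatment plan. Both arms receive proparacaine, then a first culture, "followed by the application of povidone-iodine to the eyelashes and eyelid margins". In the control arm, "half of the patients will be randomized to receive 5% povidone-iodine drop to the conjunctival surface followed by conjunctival culture", and then a second conjunctival PI drop. For the other arm: "The other half of patients will undergo application of another drop of topical anesthetic followed by conjunctival culture". The next sentence places that arm's conjunctival PI after the culture. Under Human subjects, the plan adds: "All cultures will be followed by application of povidone iodine".

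Data analysis and interpretation compares culture positivity between groups, together with semiquantitative grade (1+ to 4+) and species.

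**The concern.** The aim concerns a drop given after PI. The written order puts the extra drop, and the culture that follows it, before the only conjunctival PI drop that arm receives. A culture taken before conjunctival PI cannot show whether anesthetic interferes with it.

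A worse second culture in the extra-drop arm could simply reflect the missing PI drop. A similar one could reflect proparacaine's own antibacterial activity, which sections A.4 and A.5 document. Either result might still be reported as evidence on antisepsis. It could then be used to support giving anesthetic after PI, against the guideline, reported in A.6, that PI should be the last agent applied. No patient is shown to be at greater risk, because conjunctival PI still precedes every injection.

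**Working it through.** **Step 1. Lay out the written sequence** (General approach/Treatment plan; identical under Treatment plan).

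| Step | Control | Extra-drop arm |
|---|---|---|
| 1 | Proparacaine | Proparacaine |
| 2 | Culture 1 | Culture 1 |
| 3 | PI to lashes and lid margins | PI to lashes and lid margins |
| 4 | Conjunctival PI | Proparacaine |
| 5 | Culture 2 | Culture 2 |
| 6 | Conjunctival PI | Conjunctival PI |
| 7 | Injection | Injection |

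**Step 2. Count exposures.**

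| | Control | Extra-drop arm |
|---|---|---|
| Proparacaine drops before culture 2 | 1 | 2 |
| Conjunctival PI drops before culture 2 | 1 | 0 |
| Conjunctival PI drops before injection | 2 | 1 |
| Cultures after conjunctival PI then proparacaine | 0 | 0 |

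**Step 3. Look for a comparison that recovers the aim.** Interference requires conjunctival PI and the extra drop, in that order, before a culture.
- Between arms at culture 2: conjunctival PI versus a second proparacaine drop without it. Two factors change together.
- Culture 1 to culture 2 in the extra-drop arm: no conjunctival PI.
- Culture 1 to culture 2 in control: no extra drop.

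None isolates the effect of a drop given after PI, and a larger sample would not change that.

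**Step 4. Give a sense of scale.** The plan states no rates, margin, alpha or power for the cultures, so there is no planned figure to reproduce.
- Section A.4 gives 4/40 = 10% positive after proparacaine; the exact (Clopper-Pearson) 95% CI is 2.8% to 23.7%. Sixty patients in two halves is 30 per arm, so 0.10 × 30 = 3 positives. Multiplying the CI limits by 30 gives 0.8 to 7.1. This assumes the rate carries over to two drops plus lid PI.
- No positivity rate after conjunctival PI is given. Assuming 0% to 10%, control has 0 to 3 of 30.
- Newcombe 95% CIs for extra-drop minus control: 3/30 v 0/30 is +10 points (−3.1 to +25.6); 3/30 v 3/30 is 0 points (−16.9 to +16.9).

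Section A.3 also cites colony reductions of 91% with one PI drop and 33% in control eyes. The residual fractions are 9% and 67%, a ratio of 0.67/0.09 ≈ 7.4. As an illustration only, that is the difference the missing PI drop alone might produce; proparacaine's own activity could narrow it by an unknown amount.

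**The case against.** The strongest reply is that Figure 1, the plan's own step diagram, could not be seen, and the procedure text is the same paragraph printed twice. Since the aims put the drop after PI, a PI step may simply have been left out of the text. That is possible, so the conclusion applies to the text as written. If the figure differs, the text is still wrong in two places and staff could follow either order.

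Second, antisepsis can be read broadly. If culture 2 without conjunctival PI were about as clean as control after PI, that would be partly reassuring about the bacteria left on the eye. This stands for that broader question, and the cultures do partly serve the proparacaine with-and-without-PI purpose in A.6 and under Data collection. It does not exclude dilution of PI or antagonism. The in-vitro findings in A.5 (synergy against viridans streptococci, additivity or indifference against *S. epidermidis*) are background and do not replace the clinical check.

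Third, lid-margin PI precedes the extra drop and some may spread to the conjunctiva. True, but it is common to both arms and is not the conjunctival drop that control receives before culture 2.

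Finally, patient experience is the lead aim and patients are protected by the final PI. Both points are correct. They limit the harm but do not make the antisepsis claim testable.

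**Conclusion.** The concern holds. On the written sequence, the stated culture aim cannot be met: conjunctival PI exposure at culture 2 is 1 v 0 drops, proparacaine is 1 v 2, and the sequence of interest is never cultured. For the interference question, any culture 2 difference or null result is uninterpretable, and analysis cannot repair this.

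This rests on the order of steps alone. The 3/30 and 0 to 3/30 illustrations rest on the assumed rates and show only that plausible results, from 0 to +10 points, would carry no information about interference. The one reservation is that Figure 1 may give a different order. The correction is needed before the cultures are used to support any statement about antisepsis.

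**What to change.** First check Figure 1 and the procedure staff will follow. Then take one of two routes.

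1. **The written order stands.** Restate the culture comparison as positivity after conjunctival PI versus after a second proparacaine drop without conjunctival PI. Remove the non-interference claim from the Introductory Statement, and align the antisepsis assurances in the Study rationale and Indication. The patient-experience aim needs the same rewording, because it too refers to a drop after PI and the arms receive 2 v 1 conjunctival PI drops. The cost is wording and a narrower claim.

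2. **A PI step was left out.** Correct both procedure sections so the extra-drop arm reads: conjunctival PI, proparacaine, culture 2, conjunctival PI. Control stays as conjunctival PI, culture 2, conjunctival PI. Fix the same interval from PI to culture 2 in both arms. The planned drops then differ only in the extra proparacaine, with 2 v 2 conjunctival PI drops before injection, which also repairs the patient-experience contrast. The cost is one more PI drop in that arm than now written, in a trial citing PI as the most bothersome step for 26% of patients. No culture is added.

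Keep the final PI after culture 2 in either case; it is a stated safety step.

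Route 2 makes the question testable but does not make 30 per arm sufficient for non-inferiority. With equal true positivity p, margin m, one-sided 2.5% and 80% power, n per arm = (1.960 + 0.842)² × 2p(1 − p)/m². Power at 30 per arm uses the same normal approximation. Both p and m are assumptions.

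| p | m | n per arm | Power at 30 per arm |
|---|---|---|---|
| 5% | 20 points | 19 | 94% |
| 10% | 15 points | 63 | 49% |
| 20% | 10 points | 252 | 16% |
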